#### **7.1.2.7 Tumor Tissue Collection and Correlative Blood Sampling**

Subjects with oropharynx cancer must have an assessment of HPV status from tumor tissue (see Section 6.1.1).

All subjects will submit either a "newly obtained" core or excisional biopsy (fine needle aspirate not adequate) to a central lab for characterization of PD-L1 and HPV status, performed retrospectively. Upon receipt of the sample, the central lab will perform an H&E to confirm the sample contains sufficient tumor for PD-L1 analysis. Confirmation of tissue adequacy should be received from the central vendor prior to the first dose of trial treatment. Repeat samples may be required if adequate tissue is not provided.

A "newly obtained" sample may be obtained up to 42 days prior to treatment initiation. Tissue beyond the 42-day window may be considered with Sponsor approval as long as no intervening systemic therapy has been administered. Tissue that has been previously irradiated is acceptable. Subjects for whom newly obtained samples cannot be obtained (e.g. inaccessible or subject safety concern) may submit an archival specimen only upon agreement from the Sponsor.

Submission of tissue in formalin or embedded tumor tissue sample blocks is preferred. If submitting unstained slides, the slides should be freshly cut and submitted to the testing laboratory within 14 days from site slide sectioning date otherwise a new specimen will be requested. Detailed instructions for tissue collection, processing, and shipment are provided in the appendices of the Central Lab Manual.

Blood for correlative biomarker studies should be collected pre-dose Cycle 1, Cycle 2, Cycle 3, and again at treatment discontinuation. Detailed instructions for tissue collection, processing and shipment are provided in the appendices of the Central Lab Manual.

#### **7.1.3 Laboratory Procedures/Assessments**

Details regarding specific laboratory procedures/assessments to be performed in this trial are provided below. The total amount of blood/tissue to be drawn/collected over the course of the trial (from pre-trial to post-trial visits), including approximate blood/tissue volumes drawn/collected by visit and by sample type per patient can be found in the Procedures Manual for the study.

### 7.1.3.1 Laboratory Safety Evaluations (Hematology, Chemistry and Urinalysis)

Laboratory tests for hematology, chemistry and urinalysis are specified in [Table 7](#).

Table 7      Laboratory Tests

Hematology	Chemistry	Urinalysis	Other
Hematocrit	Albumin	Blood	Serum $\beta$ -human chorionic gonadotropin ( $\beta$ -hCG) a
Hemoglobin	Alkaline phosphatase	Glucose	PT (INR)
Platelet count	Alanine aminotransferase (ALT)	Protein	aPTT
WBC (total and differential)	Aspartate aminotransferase (AST)	Specific gravity	Total triiodothyronine (T3)/FT3 b
Red Blood Cell Count	Bicarbonate	Microscopic exam, if abnormal results are noted	Free thyroxine (T4)
Absolute Neutrophil Count	Calcium	Urine pregnancy test a	Thyroid stimulating hormone (TSH)
Absolute Lymphocyte Count	Chloride		Blood for FBR
	Creatinine		Blood for correlative studies
	Glucose		
	Phosphorus		
	Potassium		
	Sodium		
	Total Bilirubin		
	Direct Bilirubin, if total bilirubin is elevated above the upper limit of normal		
	Total protein		
	Blood Urea Nitrogen		
	Carbon dioxide (CO 2 or bicarbonate) b		
	Uric acid		
	Urea c		

a Perform on women of childbearing potential only. Serum pregnancy test is preferred but urine test can be considered if serum not appropriate.

b If considered standard of care in your region.

c Blood Urea Nitrogen is preferred; if not available urea may be tested.

Laboratory tests for screening should be performed within 10 days prior to the first dose of trial treatment. After Cycle 1, pre-dose laboratory procedures can be conducted up to 72 hours prior to dosing. Results must be reviewed by the investigator or qualified designee and found to be acceptable prior to each dose of trial treatment.

### **7.1.3.2 Pharmacokinetic/Pharmacodynamic Evaluations**

To evaluate the immunogenicity of and exposure to pembrolizumab in this indication, sample collections for analysis of anti-pembrolizumab antibodies (ADA) and PK are currently planned as shown in Section 6.1-Initial Treatment Phase and Second Course Phase (Retreatment).C. Blood samples for PK and ADA that are collected may be only stored at this time. Further analysis may be performed if required. If ongoing PK and/or ADA sampling is deemed unnecessary by the Sponsor, it may be reduced or discontinued.

#### **7.1.3.2.1 Blood Collection for Serum MK-3475**

Sample collection, storage and shipment instructions for serum PK samples will be provided in the appendices of the Central Lab Manual.

#### **7.1.3.2.2 Blood Collection for Anti-Pembrolizumab Antibodies**

Sample collection, storage and shipment instructions for anti- pembrolizumab (MK-3475) antibody samples will be provided in the appendices of the Central Lab Manual. Anti-pembrolizumab (MK-3475) antibody samples should only be drawn for all study subjects participating in the study.

### **7.1.3.3 Future Biomedical Research**

The following specimens are to be obtained as part of Future Biomedical Research:

- Leftover DNA
- Leftover tumor tissue

### **7.1.4 Other Procedures**

#### **7.1.4.1 Withdrawal/Discontinuation**

When a subject discontinues/withdraws from participation in the trial, all applicable activities scheduled for the end of treatment visit should be performed at the time of discontinuation. Any adverse events which are present at the time of discontinuation/withdrawal should be followed in accordance with the safety requirements outlined in Section 7.2 - Assessing and Recording Adverse Events. Subjects who a) attain a CR or b) complete 24 months of treatment with pembrolizumab (MK-3475) may discontinue treatment with the option of restarting treatment if they meet the criteria specified in Section 7.1.5.2.1. After discontinuing treatment following assessment of CR or 24 months of treatment, these subjects should return to the site for a Safety Follow-up Visit (described in Section 7.1.5.3.1) and then proceed to the Follow-up Period of the study (described in Section 7.1.5.3.2).

#### **7.1.4.1.1 Withdrawal From Future Biomedical Research**

Subjects may withdraw their consent for Future Biomedical Research and have their specimens and all derivatives destroyed. Subjects may withdraw consent at any time by contacting the principal investigator for the main trial. If medical records for the main trial are still available, the investigator will contact the Sponsor using the designated mailbox ([contact]), and a form will be provided by the Sponsor to obtain appropriate information to complete specimen withdrawal. Subsequently, the subject's specimens will be removed from the biorepository and be destroyed. A letter will be sent from the Sponsor to the investigator confirming the destruction. It is the responsibility of the investigator to inform the subject of completion of destruction. Any analyses in progress at the time of request for destruction or already performed prior to the request being received by the Sponsor will continue to be used as part of the overall research trial data and results. No new analyses would be generated after the request is received.

In the event that the medical records for the main trial are no longer available (e.g., if the investigator is no longer required by regulatory authorities to retain the main trial records) or the specimens have been completely anonymized, there will no longer be a link between the subject's personal information and their specimens. In this situation, the request for specimen destruction cannot be processed.

#### **7.1.4.2 Blinding/Unblinding**

This is an open label trial; there is no blinding for this trial.

#### **7.1.4.3 Calibration of Critical Equipment**

The investigator or qualified designee has the responsibility to ensure that any critical device or instrument used for a clinical evaluation/test during a clinical trial that provides important information about inclusion/exclusion criteria and/or safety or efficacy parameters shall be suitably calibrated and maintained to ensure that the data obtained is reliable and/or reproducible. Documentation of equipment calibration must be retained as source documentation at the trial site.

Critical Equipment for this trial includes:

- Laboratory equipment – as required for inclusion labs and trial assessments

See protocol-specified guidance in the Administrative Binder, and the Central Lab Manual.

#### **7.1.5 Visit Requirements**

Visit requirements are outlined in Section 6.0 - Trial Flow Chart. Specific procedure-related details are provided above in Section 7.1 - Trial Procedures.

### 7.1.5.1 Screening

Approximately 28 days prior to subject allocation, potential subjects will be evaluated to determine that they fulfill the entry requirements as set forth in Section 5.1. Visit requirements are outlined in Section 6.0 – Trial Flow Chart.

Results of a test performed prior to the subject signing consent as part of routine clinical management are acceptable in lieu of a screening test if performed within the specified time frame. Screening procedures are to be completed within 28 days prior to the first dose trial treatment except for the following:

- Laboratory tests and ECOG PS are to be performed within 10 days prior to the first dose of trial treatment.
- For women of reproductive potential, a serum pregnancy test will be performed within 72 hours prior to the first dose of trial treatment. A urine test may be considered if serum test is not appropriate.
- A “newly obtained” tissue sample is not required to be obtained within 28 days prior to the first dose of trial treatment. The sample should be obtained within 42 days of the first dose. See Section 7.1.2.7 for additional details regarding tumor tissue requirements.

Subjects may be rescreened after initially failing to meet the inclusion/exclusion criteria. Results from assessments performed during the initial screening period are acceptable in lieu of a repeat screening test if performed within the specified time frame and the inclusion/exclusion criteria is met.

### 7.1.5.2 Treatment Period

Visit requirements are outlined in Section 6.0 – Trial Flow Chart. Specific procedure-related details are provided above in Section 7.1 – Trial Procedures.

#### 7.1.5.2.1 Second Course Phase (Retreatment Period)

Subjects who stop pembrolizumab (MK-3475) with SD or better may be eligible for up to one year of additional MK-3475 therapy if they progress after stopping study treatment. This retreatment is termed the Second Course Phase of this study and is only available if the study remains open and the subject meets the following conditions:

- Either
  - Stopped initial treatment with pembrolizumab (MK-3475) after attaining an investigator-determined confirmed CR according to RECIST 1.1
    - Was treated for at least 24 weeks with pembrolizumab (MK-3475) before discontinuing therapy AND
    - Received at least two treatments with pembrolizumab (MK-3475) beyond the date when the initial CR was declared

**OR**

- Had SD, PR or CR and stopped pembrolizumab (MK-3475) treatment after 24 months of study therapy for reasons other than disease progression or intolerance

**AND**

- Experienced an investigator-determined confirmed radiographic disease progression after stopping their initial treatment with pembrolizumab (MK-3475)
- Did not receive any anti-cancer treatment since the last dose of pembrolizumab (MK-3475)
- Has a performance status of 0 or 1 on the ECOG Performance Scale
- Demonstrates adequate organ function as detailed in Section 5.1.2
- Female subject of childbearing potential should have a negative serum or urine pregnancy test within 72 hours prior to receiving retreatment with study medication.
- Female subject of childbearing potential should be willing to use 2 methods of birth control or be surgically sterile, or abstain from heterosexual activity for the course of the study through 120 days after the last dose of study medication (Reference Section 5.7.2). Subjects of child bearing potential are those who have not been surgically sterilized or have been free from menses for > 1 year.
- Male subject should agree to use an adequate method of contraception starting with the first dose of study therapy through 120 days after the last dose of study therapy.
- Does not have a history or current evidence of any condition, therapy, or laboratory abnormality that might interfere with the subject's participation for the full duration of the trial or is not in the best interest of the subject to participate, in the opinion of the treating investigator.

Subjects who restart treatment will be retreated at the same dose frequency as when they last received pembrolizumab (MK-3475). Treatment will be administered for up to one additional year.

Visit requirements are outlined in Section 6.0 – Trial Flow Chart.

### **7.1.5.3 Post-Treatment Visits**

#### **7.1.5.3.1 Safety Follow-up Visit**

The mandatory Safety Follow-Up Visit should be conducted approximately 30 days after the last dose of trial treatment or before the initiation of a new anti-cancer treatment, whichever comes first. All AEs that occur prior to the Safety Follow-Up Visit should be recorded.

Subjects with an AE of Grade > 1 will be followed until the resolution of the AE to Grade 0-1 or until the beginning of a new anti-cancer therapy, whichever occurs first. SAEs that occur within 90 days of the end of treatment or before initiation of a new anti-cancer treatment should also be followed and recorded.

Subjects who are eligible for retreatment with pembrolizumab (MK-3475) (as described in Section 7.1.5.2.1) may have up to two safety follow-up visits, one after the Treatment Period and one after the Second Course Phase.

#### **7.1.5.3.2 Follow-up Visits**

Subjects who discontinue trial treatment for a reason other than radiographic disease progression will move into the Follow-Up Phase and should be assessed every 6 weeks (42 ±7 days) by radiologic imaging to monitor disease status. After 1 year, the imaging time point will occur every 9 weeks (±7 days). Every effort should be made to collect information regarding disease status until the start of new anti-cancer therapy, radiographic disease progression, death, end of study or if the subject begins retreatment with pembrolizumab (MK-3475) as detailed in Section 7.1.5.2.1. Information regarding post-study anti-cancer treatment will be collected if new treatment is initiated. If imaging assessment beyond the protocol-required imaging time frame is necessary for the subject's continued participation in the follow-up phase of the study, an extended imaging schedule may be considered at the discretion of the investigator. Please refer to Section 6.1-Initial Treatment Phase and Second Course Phase (Retreatment) .

Subjects who are eligible to receive retreatment with pembrolizumab (MK-3475) according to the criteria in Section 7.1.5.2.1 will move from the Follow-Up Phase to the Second Course Phase when they experience disease progression. Details are provided in Section 6.1.2 – Second Course Phase (Retreatment) for Pembrolizumab (MK-3475).

#### **7.1.5.3.3 Survival Follow-up**

Once a subject experiences confirmed disease progression or starts a new anti-cancer therapy, the subject moves into the Survival Follow-Up Phase and should be contacted by telephone approximately every 12 weeks to assess for survival status until death, withdrawal of consent, or the end of the study, whichever occurs first.

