## 6.0 TRIAL FLOW CHART

### 6.1 Initial Treatment Phase and Second Course Phase (Retreatment)

#### 6.1.1 Initial Treatment Phase

Trial Period:	Screening Phase	Treatment Cycles a						End of Treatment	Post-Treatment		
		1	2	3	4	To be repeated beyond 6 cycles		Discon	Safety Follow-up	Follow Up Visits b	Survival Follow-up c
Treatment Cycle/Title:	Screening (Visit 1)					5	6				
Scheduling Window (Days) d :	-42 to -1	-28 to -1	+3 d	± 3	± 3	± 3	± 3	At time of discon	30 days post discon	Every 6 weeks post discon	Approx. every 12 weeks
Administrative Procedures											
Informed Consent	X e										
Informed Consent for Future Biomedical Research		X f									
Inclusion/Exclusion Criteria		X									
Subject Identification Card		X									
Demographics and Medical History		X									
Prior and Concomitant Medication Review g	X	X	X	X	X	X	X	X	X		
Trial Treatment Administration h		X	X	X	X	X	X				
Post-study Anticancer Therapy Status										X	X
Survival Status c											X
Clinical Procedures/Assessments											
Review Adverse Events	X	X	X	X	X	X	X	X	X i	X i	
12-Lead ECG (Local) x	X										
Full Physical Examination x	X							X			
Directed Physical Examination		X	X	X	X	X	X				
Vital Signs and Weight k	X	X	X	X	X	X	X	X	X	X	
ECOG Performance Status	X	X	X	X	X	X	X	X	X	X	
Laboratory Procedures/Assessments: analysis performed by LOCAL laboratory											
Pregnancy Test – Serum or Urine l		X									
PT/INR and aPTT m		X n									
CBC with Differential o		X n		X	X	X	X	X	X p		
Chemistry Panel o		X n		X	X	X	X	X	X p		

Trial Period:	Screening Phase	Treatment Cycles a						End of Treatment	Post-Treatment		
		1	2	3	4	To be repeated beyond 6 cycles		Discon	Safety Follow-up	Follow Up Visits b	Survival Follow-up c
Treatment Cycle/Title:	Screening (Visit 1)					5	6				
Scheduling Window (Days) d :	-42 to -1	-28 to -1	+3 d	± 3	± 3	± 3	± 3	At time of discon	30 days post discon	Every 6 weeks post discon	Approx. every 12 weeks
Urinalysis o		X n		X		X	X t		X p		
T3, FT4 and TSH o		X n		X		X	X t		X p		
HPV Status w	X										

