prior to the first dose of trial treatment for required lab tests). Screening number will be assigned when the study informed consent is signed. 
 
f. Signing the informed consent for future biomedical research (FBR) sample is optional. Detailed instructions for the collection and management of specimens for FBR are provided in the appendices of the Central Lab Manual and Section 12.2 of the Protocol.
 
g. Prior medications – Record all medications taken within 30 days of the screening visit. Concomitant medications – Enter new medications started during the trial through the Safety Follow-up visit. Record all medications taken for SAEs as defined in Section 7.2.
 
h. Trial treatment may be administered up to 3 days before or after the scheduled Day 1 of each cycle due to administrative reasons. Sites should make every effort to target infusion timing to be as close to 30 minutes as possible. However, given the variability of infusion pumps from site to site, a window of -5 minutes and +10 minutes is permitted (i.e., infusion time is 30 minutes: -5 min/+10 min). The reason for any delay in infusion outside of the protocol specified window should be documented in the patient's chart and recorded on the eCRFs.
 
i. Record all AEs occurring within 30 days after the last dose of trial treatment. Report all SAEs (related and unrelated to trial treatment) and ECIs occurring up until 90 days after the last dose of trial treatment or the start of new anti-cancer treatment, whichever comes first. Afterwards, report only SAEs and ECIs that are related to trial treatment.
 
j. To be repeated every 2 cycles after Cycle 6 up to 1 year.
 
k. Vital signs to include temperature, pulse, respiratory rate, weight and blood pressure. Height will be measured at visit 1 only.
 
l. For women of reproductive potential, a serum pregnancy test should be performed within 72 hours prior to first dose of trial treatment. A urine test can be considered if serum is not appropriate. Pregnancy tests (serum and/or urine tests) should be repeated if required by local guidelines.
 
m. Coagulation factors (PT/INR and aPTT) should be tested as part of the screening procedures for all subjects. Any subject receiving anticoagulant therapy should have coagulation factors monitored closely throughout the trial.
 
n. Laboratory tests for screening are to be performed within 10 days prior to the first dose of trial treatment. See Section 7.1.3 for details regarding laboratory tests.
 
o. After Cycle 1, lab samples can be collected up to 72 hours prior to the scheduled time point. See Section 7.1.3 for details regarding laboratory tests.
 
p. Unresolved abnormal labs that are drug related AEs should be followed until resolution. Labs do not need to be repeated after the end of treatment if labs are within normal range.
 
q. Pre-dose trough PK and anti-pembrolizumab (MK-3475) antibody samples will be collected at Cycles 1, 2, 4, 8, and every 4 cycles thereafter. All pre-dose trough samples should be drawn within 24 hours before infusion of pembrolizumab (MK-3475). Additional post-dose peak PK samples will be drawn within 30 minutes after end of pembrolizumab (MK-3475) infusion at Cycles 1 and 8. An additional, single PK sample should be drawn between 72 and 168 hours after Cycle 1 dosing.
 
r. Blood for correlative studies should be collected prior to Cycle 1, Cycle 2, Cycle 3 and again at treatment discontinuation.
 
s. The initial tumor imaging will be performed within 28 days prior to the first dose of trial treatment and must be sent to the central vendor to confirm measurable disease for study eligibility. Imaging should include the head, neck, chest, and abdomen; imaging of the pelvis is optional (refer to Section 7.1.2.6). Scans performed as part of routine clinical management are acceptable for use as the screening scan if they are of diagnostic quality, meet the requirements specified by the protocol, and are performed within 28 days prior to the first dose of trial treatment.
 
t. The first on-study imaging time point will be performed at 9 weeks (± 7 days) after first dose of study treatment and then every 6 weeks (± 7 days) thereafter or more frequently if clinically indicated. After 1 year, imaging time point will occur every 9 weeks (± 7 days). Imaging timing should follow calendar days and should not be adjusted for delays in cycle starts or extension of pembrolizumab (MK-3475) cycle frequencies. Imaging should include the head, neck, chest, and abdomen; imaging of the pelvis is optional (refer to Section 7.1.2.6). The same imaging technique should be used in a subject throughout the trial. On-study scans, including the baseline scans, should be submitted immediately to the central imaging vendor.
 
u. Baseline tumor tissue for biomarker analysis from a newly obtained core or excisional biopsy (FNA not adequate) must be provided to the central vendor for PD-L1 biomarker testing. Confirmation of tissue adequacy should be received from the central vendor prior to the first dose of trial treatment. A “newly obtained” sample may be obtained up to 42 days prior to
 
											

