### **7.2.3 Immediate Reporting of Adverse Events to the Sponsor**

#### **7.2.3.1 Serious Adverse Events**

A serious adverse event is any adverse event occurring at any dose or during any use of Sponsor's product that:

- Results in death;
- Is life threatening;
- Results in persistent or significant disability/incapacity;
- Results in or prolongs an existing inpatient hospitalization;

- Is a congenital anomaly/birth defect;
- Is a new cancer (that is not a condition of the study);
- Is associated with an overdose;
- Is an other important medical event

Refer to [Table 8](#) for additional details regarding each of the above criteria.

For the time period beginning when the consent form is signed until treatment allocation, any serious adverse event, or follow up to a serious adverse event, including death due to any cause, other than progression of the cancer under study (reference Section 7.2.3.3 for additional details), that occurs to any subject must be reported within 24 hours to the Sponsor if it causes the subject to be excluded from the trial, or is the result of a protocol-specified intervention, including but not limited to washout or discontinuation of usual therapy, diet, placebo treatment or a procedure.

For the time period beginning at treatment allocation through 90 days following cessation of treatment, or 30 days following cessation of treatment if the subject initiates new anticancer therapy, whichever is earlier, any serious adverse event, or follow up to a serious adverse event, including death due to any cause other than progression of the cancer under study (reference Section 7.2.3.3 for additional details), whether or not related to the Sponsor's product, must be reported within 24 hours to the Sponsor either by electronic media or paper. Electronic reporting procedures can be found in the EDC data entry guidelines. Paper reporting procedures can be found in the Investigator Trial File Binder (or equivalent).

Additionally, any serious adverse event, considered by an investigator who is a qualified physician to be related to the Sponsor's product that is brought to the attention of the investigator at any time following consent through the end of the specified safety follow-up period specified in the paragraph above, or at any time outside of the time period specified in the previous paragraph also must be reported immediately to the Sponsor.

All subjects with serious adverse events must be followed up for outcome.

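### Survival Follow-up schedules no SAE or ECI enquiry, so late events in subjects who leave with progression depend on passive reporting up to Day 90

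*Combined protocol and SAP*

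**What the plan says.** **Collection windows.** Footnote i of the flow chart in 6.1.1 asks sites to "Record all AEs occurring within 30 days after the last dose of trial treatment". It then says "Report all SAEs (related and unrelated to trial treatment) and ECIs occurring up until 90 days after the last dose of trial treatment", or until new anti-cancer treatment starts if that is sooner. Section 7.2.3.1 sets the SAE period "through 90 days following cessation of treatment, or 30 days following cessation of treatment if the subject initiates new anticancer therapy, whichever is earlier", and 7.2.3.2 applies the same limits to ECIs.

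**Last visit common to all.** Section 7.1.5.3.1: "The mandatory Safety Follow-Up Visit should be conducted approximately 30 days after the last dose of trial treatment", or ahead of new therapy if that comes first.

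**What follows depends on the reason for stopping.** Section 7.1.5.3.2: "Subjects who discontinue trial treatment for a reason other than radiographic disease progression will move into the Follow-Up Phase", with imaging at 42 ± 7 days. For confirmed progression or new therapy, 7.1.5.3.3 states that "the subject moves into the Survival Follow-Up Phase and should be contacted by telephone approximately every 12 weeks to assess for survival status".

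**Where adverse events are reviewed.** The "Review Adverse Events" row is marked through the Follow Up Visits column and is empty under Survival Follow-up. This is clearest in 6.1.2. In 6.1.1 the Follow Up Visits cell carries footnote i, so that visit is used to collect late SAEs and ECIs.

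**The concern.** The plan collects SAEs and ECIs to Day 90 but gives only some subjects a scheduled occasion on which anyone asks about them after about Day 30. The dividing line is the reason for leaving treatment. A subject who stops for toxicity, say, returns to visits with an adverse event review. A subject who stops for confirmed progression gets a call about survival.

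Safety and tolerability is the first primary objective (3.1), and 8.2.3.2 includes SAEs and ECIs in its assessment. Section 5.2.1.2 warns that immune-related events can first appear months after dosing stops, so late events are not a remote possibility. With one arm, the absolute rates are the safety result, and no comparator collected in the same way is there to offset missed events. What is at stake is possible under-ascertainment of late SAEs and ECIs, differing by exit reason.

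**Working it through.** The plan states no figure for this point, so the check is schedule arithmetic.

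**Inputs.** The safety visit is at about Day 30 (7.1.5.3.1). The SAE/ECI window ends at Day 90 (6.1.1 footnote i). Follow-Up visits are every 42 days (7.1.5.3.2), and imaging may be stretched to every 12 weeks in year 1 (6.1.1 footnote b). Survival calls are about every 84 days (7.1.5.3.3). Let L be the days from last dose to discontinuation (Follow-Up Phase) or to documented progression (Survival Follow-up). Two assumptions: intervals are taken at nominal length and start at L, and under the extension the adverse event review moves with the imaging visit.

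**Days without a universal visit.** 90 − 30 = 60 days; 60/90 = 67% of the window.

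**Contacts in Days 31-90.** Follow-Up visits fall at L + 42 and L + 84. The second is inside the window only if L + 84 ≤ 90, that is L ≤ 6. The first survival call also falls at L + 84.

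| L | Follow-Up visits (day) | AE reviews in Days 31-90 | Same, 12-week extension | Survival call (day) | AE reviews in Days 31-90, Survival Follow-up |
|---|---|---|---|---|---|
| 0 | 42, 84 | 2 | 1 | 84 | 0 |
| 6 | 48, 90 | 2 | 1 | 90 | 0 |
| 7 | 49, 91 | 1 | 0 | 91 | 0 |
| 21 | 63, 105 | 1 | 0 | 105 | 0 |
| 42 | 84, 126 | 1 | 0 | 126 | 0 |

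The last column is zero whatever L is, because a survival call carries no adverse event review even when it falls inside the window.

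**Window after new therapy.** Three rules appear:
- 6.1.1 footnote i: to the start of new treatment
- 6.1.2 footnote i: to 30 days after that start
- 7.2.3.1 and 7.2.3.2: to 30 days after cessation of study treatment

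Each is capped at Day 90. Take a subject who progressed and starts new therapy on Day 80, with cessation counted from the last dose:
- first rule: Days 31-80 are open with no scheduled review (50 days)
- second rule: 80 + 30 = 110, capped at 90, so Days 31-90 (60 days)
- third rule: the window closed at Day 30, so none

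**Possible size, on assumptions only.** Events missed = 150 × f × q × m. Here f is the share who progress without new therapy, q the true Day 31-90 SAE/ECI risk, and m the share not reported. None of the three is in the documents.
- Low: 150 × 0.20 × 0.05 × 0.10 = 0.15 subjects (0.1 percentage points)
- Middle: 150 × 0.40 × 0.10 × 0.30 = 1.8 subjects (1.2 points)
- High: 150 × 0.60 × 0.20 × 0.50 = 9 subjects (6.0 points)

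**The case against.** The strongest reply is that collection after Day 30 is passive, not absent. SAEs and ECIs inside the window must reach the sponsor within 24 hours, related or not (7.2.3.1, 7.2.3.2). SAEs to Day 90 are to be followed and recorded, and any event above Grade 1 is followed until it settles or new therapy begins (7.1.5.3.1). These duties apply whatever the exit reason. Under 7.2.3.1 and 7.2.3.2, starting new therapy cuts the window to 30 days, which the safety visit covers. Collection of all adverse events to Day 30 is uniform, so only SAEs and ECIs with onset in Days 31-90 are exposed. There is one arm, so no treatment comparison is distorted. The Follow-Up Phase can itself thin to 12-weekly imaging.

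All of this stands and limits the point. It does not remove it, because a duty to report does not by itself detect an event. Section 7.2.3.2 ties the check for ECIs to each dose, and that prompt ends with treatment. Some ECIs are non-serious and may not surface unasked. Section 7.2.3.3 exempts progression from SAE reporting, so a late admission in a subject who has progressed could be put down to the cancer.

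Three stronger readings are tempting and are not supported:
- A reader might infer that SAE and ECI incidence is biased downward. The documents show a route to under-ascertainment but no missed events.
- A reader might scale up the earlier phase Ib trial in Section 4.1.3, where 56 − 11 responders − 16 with stable disease leaves 29 of 56. Best response is not exit reason, those 29 are not described as confirmed progressors, and subjects who start new therapy are not removed.
- A reader might fix the day of the first survival call from the last dose or the safety visit. The text starts that phase at progression or new therapy and names neither as the start of the clock.

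**Conclusion.** The point holds as a gap in scheduled enquiry. Subjects who leave with progression and have not started new anti-cancer therapy have no scheduled SAE/ECI review for up to 60 of the 90 days. Subjects who leave for other reasons nominally have one or two, falling to one or none under the 12-week extension. SAE and ECI incidence may therefore be under-ascertained by exit reason.

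The size is unknown. The number exposed depends on how many progress, survive and stay off new therapy, and on which phase takes clinically unstable subjects, who need no confirmatory scan (7.1.2.6.3). The illustrative range of 0.15 to 9 subjects rests wholly on assumed inputs and is not an estimate. The efficacy analyses and adverse event collection to Day 30 are untouched. This is an inexpensive improvement to late safety collection, not a defect that undermines the safety objective.

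**What to change.** For every subject whose 90-day window is still open and who has not started new anti-cancer therapy, place one telephone contact at or just after Day 90 from the last dose. It can serve as the first survival call. Add an SAE/ECI review covering the time since the Safety Follow-up visit. Mark that review in the Survival Follow-up column of 6.1.1 and 6.1.2 and state it in 7.1.5.3.3.

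The review would rely on footnote i, so also reconcile the three wordings of the SAE/ECI window after new therapy (6.1.1 footnote i, 6.1.2 footnote i, and 7.2.3.1 with 7.2.3.2). This review takes no position on which should prevail.

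Cost: slightly less flexible timing of one call, a short script, and a few more late events to process. No visit or procedure is added. The limitation is that a single call at Day 90 relies on recall: it closes the gap in enquiry but does not add contact during Days 31-90.
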